1.3 Number of Subjects

The study will plan to enroll approximately 965 patients globally in order to randomize approximately 724 patients to 1 of 3 treatment groups: durvalumab monotherapy (approximately 262 patients), placebo (approximately 262 patients), or durvalumab + tremelimumab combination therapy (approximately 200 patients) over a period of approximately 38 months. Initially, patients will be randomized 1:1:1 to the 3 treatment groups. Following implementation of CSP Version 4, once 600 patients have been randomized, a further 124 patients will subsequently be randomized 1:1 to durvalumab monotherapy or placebo until a total of approximately 724 patients have been randomized.

The study has dual primary objectives which are to assess the efficacy of durvalumab monotherapy compared to placebo in terms of PFS per RECIST 1.1 as assessed by BICR, and OS.

The primary PFS analysis will occur at the earliest of:

- 1. When approximately 370 PFS BICR events have occurred (70.6% maturity) in the durvalumab monotherapy and placebo treatment groups
- 2. At OS-IA2, if OS-IA2 is statistically significant (durvalumab monotherapy vs placebo)
- 3. Approximately 36 months after the last patient randomized

If the true PFS HR is 0.65 for durvalumab monotherapy versus placebo, with 370 PFS BICR events, the study will have approximately 90% power to demonstrate a statistically significant difference in PFS between durvalumab monotherapy and placebo, with an overall 2-sided significance level of 0.5%. The true HR of 0.65 translates to a 5.4 month benefit in median PFS over 10 months on placebo if PFS is exponentially distributed. The smallest treatment difference that would be statistically significant is a HR of 0.743 (Critical value (CV)). At this time, approximately 309 PFS BICR events are also expected to have occurred in the durvalumab in combination with tremelimumab and placebo treatment groups. A recruitment period of approximately 38 months was assumed in the CSP for the primary PFS analysis.

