3.3.1.3 QLQ-C30 and QLQ-LC13 symptom improvement rate

The symptom improvement rate will be defined as the number (%) of patients with a minimum of 2 consecutive assessments at least 14 days apart that show a clinically meaningful improvement (a decrease from baseline score ≥ 10 for symptom scales/items) in that symptom from baseline. Missed visits are not allowed in between consecutive assessments of improvement. This is considered a conservative approach whereby an

improvement is considered a 'positive' outcome and therefore for any avoidance of doubt in the assessment of an improvement, missed visits are not allowed.

When the assessment schedule is weekly i.e. QLQ-LC13 weeks 1 to 8, an improvement needs to be observed at each assessment that falls within the 14 day interval to be classed as an improvement. For example:

V1	V2	V3	V4	Outcome
(Week 1)	(Week 2)	(Week 3)	(Week 4)	
IMP	IMP	IMP	NC	Improvement
IMP	IMP	NC	DT	No improvement*
IMP	MV	IMP	IMP	No improvement*
NC	IMP	NC	IMP	No improvement*

DT Deterioration; IMP Improvement; MV Missed visit. NC No change.

The denominator will consist of a subset of the FAS who have a baseline symptom score ≥ 10 .

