3.3.1.4 QLQ-C30 GHS/QoL/functional improvement rate

The GHS/QoL/functional improvement rate will be defined as the number (%) of patients with 2 consecutive assessments at least 14 days apart that show a clinically meaningful improvement (an increase from baseline score ≥10 for functional scales and GHS/QoL) in that scale from baseline. Missed visits are not allowed in between consecutive assessments of improvement. This is considered a conservative approach whereby an improvement is considered a 'positive' outcome and therefore for any avoidance of doubt in the assessment of an improvement, missed visits are not allowed.

The denominator will consist of a subset of the FAS who have a baseline score <90.

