4.2 Analysis Methods

Results of all statistical analyses will be presented using a 95% confidence interval (CI) and 2-sided p-value, unless otherwise stated.

Table 7 details which endpoints are to be subject to formal statistical analysis, together with pre-planned sensitivity analyses making clear which analysis is regarded as primary for that endpoint. Note, all efficacy endpoints (including PROs) comparing durvalumab monotherapy with placebo will be in all randomized patients (FAS). Efficacy analyses comparing durvalumab and tremelimumab combination therapy with placebo, and durvalumab monotherapy with durvalumab and tremelimumab combination therapy, will be in the combination analysis set, unless otherwise indicated.

Table 7 Pre-planned statistical and sensitivity analyses to be conducted

Endpoints Analyzed Notes	
Progression-free survival	Stratified log-rank tests for:
	 Primary analysis using BICR assessments (RECIST 1.1) for durvalumab monotherapy versus placebo
	 Sensitivity analyses using BICR assessments (RECIST 1.1)
	1) Interval censored analysis – evaluation time bias
	2) Analysis using alternative censoring rules – attrition bias
	 Sensitivity analysis using site Investigator assessments (RECIST 1.1) – ascertainment bias
	 Secondary analysis using BICR assessments (RECIST 1.1) for durvalumab + tremelimumab versus placebo and durvalumab monotherapy versus durvalumab + tremelimumab)
	Subgroup analysis using Cox proportional hazards models
	Additional analysis using Cox proportional hazards models to determine the effect of covariates on the HR estimate
	Additional analysis using Cox proportional hazards models to determine the consistency of treatment effect between subgroups via the approach of Gail and Simon 1985.
Overall survival	Stratified log-rank tests for:
	 Primary analysis (durvalumab monotherapy versus placebo)
	 Secondary analysis (durvalumab + tremelimumab versus placebo and durvalumab monotherapy versus durvalumab + tremelimumab)
	Sensitivity analysis using a Kaplan-Meier plot of time to censoring where the censoring indicator of the primary analysis is reversed – attrition bias
	Subgroup analysis using Cox proportional hazards models
	Additional analysis using Cox proportional hazards models to determine the effect of covariates on the HR estimate
	Additional analysis using Cox proportional hazards models to determine the consistency of treatment effect between subgroups via the approach of Gail and Simon 1985.

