4.2.2 Progression-free survival

The primary PFS analysis will be based on RECIST 1.1 using BICR tumor assessments. The analysis will be performed in the FAS using a stratified log-rank test (using the TEST statement in PROC LIFETEST) adjusting for TNM stage (I/II versus III) and receipt of PCI (yes versus no) for generation of the p-value and using the Efron approach for handling ties (Efron, 1977). The effect of durvalumab monotherapy and durvalumab and tremelimumab combination therapy versus placebo treatment will be estimated by the hazard ratio (HR) together with its corresponding confidence interval (CI) (95% and [1-adjusted alpha] \times 100%) from a stratified Cox proportional hazards model (Cox 1972) (with ties = Efron and the stratification variables included in the strata statement) and the CI calculated using a profile likelihood approach.

In order to ensure there are at least 5 events within each strata; if there are too few events observed in the TNM Stage I/II stratification level then TNM stage may be excluded from the stratified models leaving receipt of PCI as the sole stratification factor.

The covariates in the statistical modelling will be based on the values entered into IVRS at randomization, even if it is subsequently discovered that these values were incorrect.

Secondary PFS analysis will be performed using the same methodology as for the primary analysis.

Supportive summaries/graphs

Kaplan-Meier plots of PFS will be presented by treatment group. Summaries of the number and percentage of patients experiencing a PFS event and the type of event (RECIST 1.1 or death) will be provided along with median PFS together with its corresponding 95% CI for each treatment group. The CI for median progression-free survival will be derived based on Brookmeyer-Crowley method with log-log transformation (SAS Institute Inc. 2018).

The assumption of proportionality will be assessed for each treatment comparison firstly by examining plots of complementary log-log (event times) versus log (time) and, if these raise concerns, by fitting a time-dependent covariate to assess the extent to which this represents random variation. If lack of proportionality is found, this may be a result of treatment-by-covariate interactions.

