The MMRM model will include the fixed, categorical effects of treatment, visit, and treatment-by-visit interaction, TNM stage (I/II versus III) and receipt of PCI (yes versus no) as well as the continuous fixed covariate of baseline score and the baseline score-by-visit interaction. Restricted maximum likelihood (REML) estimation will be used. An overall adjusted mean estimate will be derived that will estimate the average treatment effect over visits giving each visit equal weight. For this overall treatment comparison, adjusted mean estimates per treatment group and corresponding 95% CIs will be presented along with an estimate of the treatment difference, 95% CI and p-value.

An unstructured covariance matrix will be used to model the within-patient error and the Kenward-Roger approximation will be used to estimate the degrees of freedom. If the fit of the unstructured covariance structure fails to converge, the following covariance structures will be tried in order until convergence is reached: toeplitz with heterogeneity, autoregressive with heterogeneity, toeplitz, autoregressive and compound symmetry.

Multiple imputation techniques for missing values may be considered to explore the robustness of any treatment effect.

Time to deterioration

Time to symptom, functioning and GHS/QoL deterioration will be analyzed for each of the symptom scales/items, functional scales, and GHS/QoL in EORTC QLQ-C30 and QLQ-LC13. This will be achieved by comparing between treatment groups using a stratified log-rank test as described for the primary analysis of PFS. The HR and 95% CI for each scale/item will be presented graphically on a forest plot.

For each of the symptom scales/items, functional scales, and GHS/QoL, time to deterioration will be presented using a Kaplan-Meier plot. Summaries of the number and percentage of

patients experiencing a clinically meaningful deterioration or death and the median time to deterioration will also be provided for each treatment group.

Symptom and function and GHS/QoL improvement rate

A summary of the symptom improvement rate for all symptom scales/items in EORTC QLQ-C30 and QLQ-LC13 will be produced. Similarly, a summary of improvement rate for each of the 5 function scales (physical, role, emotional, cognitive, and social) and GHS/QoL will be produced.

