Symptom, functional and GHS/QoL improvement rates will be analyzed by comparing between treatment groups using a logistic regression model adjusting for the same factors as the PFS endpoint. The results of the analysis will be presented in terms of an odds ratio together with its associated profile likelihood 95% CI and p-value (based on twice the change in log-likelihood resulting from the addition of a treatment factor to the model). The odds ratio and 95% CI for each scale/item will be presented graphically on a forest plot. If there are very few responses in 1 treatment group, a Fisher's exact test will be considered.

Change from baseline

Summaries of original and change from baseline values of each symptom scale/item, the GHS/QoL score, and each functional domain will be reported by assessment timepoint for each treatment group. Graphical presentations may also be produced as appropriate. Summaries of the number and percentage of patients in each response category at each assessment timepoint for each ordinal item (in terms of the proportion of patients in the categories of improvement, no change, and deterioration as defined in Table 6) will also be produced for each treatment group.

A summary of compliance rate and evaluability rate will be provided for each treatment group, by assessment time point and also for overall. The summary will be provided for the FAS, combination analysis set, and patients who have discontinued treatment.

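### The improvement-rate logistic models omit the patient's baseline score, which the MMRM for the key scales includes; this costs some precision in supportive PRO analyses

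*SAP*

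**What the plan says.** SAP 4.2.11.1 analyses symptom, functional and GHS/QoL improvement rates "using a logistic regression model adjusting for the same factors as the PFS endpoint". SAP 4.2.2 defines those factors: the PFS log-rank test is run "adjusting for TNM stage (I/II versus III) and receipt of PCI (yes versus no"), and TNM stage may be dropped if Stage I/II has too few events. The improvement-rate result is an odds ratio with a profile-likelihood 95% CI and a p-value "based on twice the change in log-likelihood resulting from the addition of a treatment factor to the model". Fisher's exact test is considered if one arm has very few responses.

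Improvement is a change of at least 10 points from the patient's own baseline, in the favourable direction, at two consecutive assessments at least 14 days apart with no missed visit between them (SAP 3.3.1.3 and 3.3.1.4). For symptoms, "The denominator will consist of a subset of the FAS who have a baseline symptom score" of at least 10. For function and GHS/QoL, "The denominator will consist of a subset of the FAS who have a baseline score <90".

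The MMRM in the same SAP section covers dyspnea, cough, chest pain, fatigue, appetite loss, GHS/QoL, physical functioning and role functioning. It includes the two stratification factors "as well as the continuous fixed covariate of baseline score and the baseline score-by-visit interaction".

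Protocol 9.5.1.9 plans logistic regression for symptom improvement and names no covariates. SAP Section 6, which lists departures from the protocol, adds none.

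**The concern.** The outcome is built from the baseline score, yet the model does not contain it. Two mechanisms make baseline prognostic among eligible patients in both arms. The first is regression to the mean: a patient who starts with a bad score tends to move back. The second is the scale limit. Cough, chest pain and appetite loss are single four-level items scored 0, 33, 67 or 100. A patient at 33 can improve only by reaching 0, one at 67 by reaching 0 or 33, and one at 100 by reaching any of three lower levels.

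Omitting a prognostic covariate from a logistic model lowers the power of the treatment test. It also leaves any chance baseline difference between the arms in the reported odds ratio. The SAP accepts the argument for adjustment in the MMRM and gives no reason for treating the same scales differently here. What is at stake is the precision of the improvement-rate odds ratios on the forest plot.

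**Working it through.** **No figure to reproduce.** The documents give no power, expected improvement rate, odds ratio or baseline-outcome association for this endpoint. The question is how much the planned test gains from one added term.

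**Inputs from the documents.** The allocation is "durvalumab monotherapy (approximately 262 patients), placebo (approximately 262 patients"). SAP 4.2 sets the reporting: "Results of all statistical analyses will be presented using a 95% confidence interval (CI) and 2-sided p-value". The 10-point rule and the baseline restrictions are those of SAP 3.3.1.3 and 3.3.1.4.

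**Models compared.**

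- Planned: logit P(improve) = a + b·treatment + c1·TNM + c2·PCI
- With baseline: the same, plus d·baseline score

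In both, treatment is tested by 2 × (log-likelihood with treatment − log-likelihood without), against chi-square on 1 df at 5%.

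**Why the gain depends on correlation.** With equal SDs, the slope of change on baseline is r − 1. It is −0.7, −0.5 and −0.3 for r = 0.3, 0.5 and 0.7. A lower correlation means that baseline explains more of the change, so omitting it costs more.

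**Simulation 1: scores on the questionnaire grids.** Assumed: baseline mean 30, SD 25, improvement required at two follow-up visits, stratum shares 87% and 54%, complete follow-up. There were 262 randomized per arm and baseline had to be at least 10, leaving 184, 219 and 199 evaluable per arm for the three grids. The treatment effect was set to give roughly 80% power for the planned model; the runs gave 73% to 85%. There were 1,200 runs per row, and gains come from unrounded powers.

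| Scale | r | Improve, control / active | Baseline OR per SD | Power planned | Power with baseline | Gain (points) |
|---|---|---|---|---|---|---|
| Single item | 0.3 | 26% / 40% | 2.68 | 76.2% | 83.4% | 7.2 |
| Single item | 0.5 | 22% / 36% | 2.26 | 85.2% | 90.1% | 4.9 |
| Single item | 0.7 | 17% / 28% | 1.93 | 76.5% | 79.3% | 2.8 |
| 9-step (3 items) | 0.3 | 35% / 48% | 2.96 | 80.2% | 88.8% | 8.6 |
| 9-step (3 items) | 0.5 | 32% / 45% | 2.34 | 83.9% | 88.7% | 4.8 |
| 9-step (3 items) | 0.7 | 28% / 41% | 1.87 | 82.5% | 85.9% | 3.4 |
| 12-step | 0.3 | 28% / 41% | 2.76 | 83.8% | 89.6% | 5.8 |
| 12-step | 0.5 | 23% / 35% | 2.24 | 73.2% | 78.5% | 5.3 |
| 12-step | 0.7 | 17% / 29% | 1.81 | 81.8% | 83.3% | 1.4 |

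The 12-step row was run in the symptom direction. Reflected (score to 100 − score), it is a GHS/QoL scale with baseline mean 70 and the below-90 restriction.

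**Simulation 2: association set directly.** Assumed: 130, 200 or 262 evaluable per arm, control rate 30% or 40%, effect set for about 80% power under the planned model, 1,500 runs each.

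| Baseline OR per SD | Gain (points) |
|---|---|
| 1.25 | 0.1–0.7 |
| 1.5 | 0.2–2.5 |
| 2.0 | 2.5–3.9 |
| 2.5 | 4.8–6.8 |
| 3.0 | 7.1–10.1 |
| 4.0 | 8.1–11.5 |

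**Simulation 3: a simpler version and type I error.** Assumed: one follow-up assessment, 180 evaluable per arm, mean 30, SD 22, shift 6.5 points, 3,000 runs. At r = 0.5, power rose from 64.7% to 69.9% on a 3-item scale (+5.2) and from 59.4% to 65.5% on a single item (+6.1). The gain was 7 to 9 points at r = 0.3 and 2 to 3 at r = 0.7. With no treatment effect, on the 3-item scale, both models rejected in 4.3% of runs. The simulation error on that figure is √(0.05 × 0.95 / 3000) = 0.4 points.

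**Summary.** For r between 0.3 and 0.7, simulation 1 gives 1.4 to 8.6 points and simulation 3 gives 2 to 9, hence about 1.5 to 9. All scenarios together run from 0.1 to 11.5, quoted as about 0 to 11. Simulation error on each difference in simulations 1 and 2 is about 1 point.

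**Chance imbalance, roughly.** With 219 per arm, one standard error of the baseline difference is √(2/219) = 0.096 SD. At an OR of 2.34 per SD, such a difference multiplies the odds ratio by about exp(ln 2.34 × 0.096) = exp(0.850 × 0.096) = 1.08.

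**The case against.** The strongest reply is that the plan is sound as written and that nothing important rests on this model. Randomization keeps the planned test valid, and the simulated type I error is the same with and without baseline. Protocol 9.5.1.9 makes the MMRM of change from baseline the primary PRO assessment and calls those endpoints supportive secondary. That model already adjusts for baseline. The multiple testing procedure (SAP 4.2.1) covers only PFS and OS. All of this stands, and it fixes the weight of the point.

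A reader might infer that baseline largely decides who can improve at all. The documents do not support that: the at-least-10 and below-90 restrictions already exclude patients without room for a 10-point improvement. What remains is that baseline predicts improvement among those left.

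A reader might also take a single figure, such as 5 to 6 points, as the loss. That value appears only near a correlation of 0.5, and none of its inputs is in the documents.

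The simulations simplify the endpoint. A further run used 12 visits, the two-consecutive rule and 8% dropout per visit (all but the rule assumed; 1,000 runs). It gave gains of 6.3, 3.3 and 1.7 points on a 3-item scale and 5.2, 6.7 and 1.6 on a single item, at correlations 0.3, 0.5 and 0.7. The direction holds; the exact size is not stable.

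Finally, a linear term is an extra assumption where a single symptom item has only three eligible baseline values, and sparse items gain little from another parameter. Both are minor, because the Fisher's exact fallback is already in the plan.

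**Conclusion.** The point holds as a minor loss of efficiency. The improvement-rate models omit a prognostic covariate that is available for every patient in the denominator and that the MMRM uses for the key scales. The cost is about 1.5 to 9 power points for baseline to follow-up correlations of 0.3 to 0.7, and about 0 to 11 over all scenarios examined. It is near zero if the baseline odds ratio per SD is 1.25. These ranges rest on assumed improvement rates, effects, baseline distributions and correlations.

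It would be wrong to infer bias, loss of type I error control or any effect on the dual primary endpoints. A chance baseline imbalance can move one realised estimate, but it is not systematic. The protocol and SAP do not contradict each other here, since the protocol names no covariates for this model.

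**What to change.** In SAP 4.2.11.1, add the baseline score of the scale or item as a covariate in each symptom, function and GHS/QoL improvement-rate logistic model, alongside the PFS stratification factors. Keep the likelihood-ratio test, the profile-likelihood CI and the Fisher's exact fallback. Make the change before unblinded PRO data are seen; if that is no longer possible, report the adjusted model as a labelled supplementary analysis.

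No new data are needed and no analysed patient is lost, because baseline already defines both the outcome and the denominator. The cost is in interpretation. The odds ratio becomes conditional on baseline score, as it already is on TNM stage and PCI, and will usually lie further from 1 than the planned one. The model also assumes that the log-odds of improvement are linear in baseline.

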4.2.11.2 EQ-5D-5L

Descriptive statistics will be calculated for each scheduled time point in the study, for each treatment group and as a total. These will report the number of patients, the number of EQ-5D-5L questionnaires completed at each visit, the number and proportion responding to each dimension of the EQ-5D-5L. Additionally, summary statistics will be reported for the EQ-5D-5L index score and the EQ-5D-5L VAS score, and the change from baseline for the index and VAS scores.

A summary of compliance rate and evaluability rate will be provided for each treatment group, by assessment time point and overall.

To support submissions to payers, additional analyses may be undertaken, and these will be outlined in a separate Payer Analysis Plan.

4.2.11.3 PGIS

The number and percentage of patients in each category of the PGIS responses will be summarized by treatment group, at each assessment time point and overall.

4.2.11.4 PRO-CTCAE

The number and percentage of patients in each category of the responses for each PRO-CTCAE item will be summarized by treatment group and assessment time point.

